5.2 Secondary Endpoint

Main Cohort:

The following secondary endpoint will be evaluated for labeling purposes:

- Improvement in total PR from baseline to 30 days

5.3 Additional Safety and Effectiveness Outcomes

The following additional outcomes will be evaluated:

Main Cohort:

- Improvement in tricuspid regurgitation (TR) from baseline to 30 days and 6 months by TTE for subjects with TR of mild or greater at baseline
- Major vascular complications at 30 days and 6 months
- Life-threatening or disabling bleeding at 30 days and 6 months
- Alterra embolization at 30 days and 6 months
- THV embolization at 30 days and 6 months
- Alterra fracture that led to reintervention at 30 days and 6 months
- THV frame fracture that led to reintervention at 30 days and 6 months
- All-cause mortality at 30 days and 6 months
- Acute Device Success, defined as a non-hierarchical composite of:
 - Single Alterra deployed in the desired location
 - Single THV implanted in the desired location within Alterra (staged procedures allowed)
 - RV-PA peak-to-peak gradient < 35 mmHg post-THV implantation
 - Less than moderate total PR by discharge TTE (or earliest evaluable TTE)
 - Free of Alterra explant at 24 hours post-implantation

PDS Registry:

- Improvement in tricuspid regurgitation (TR) from baseline to 30 days by TTE for subjects with TR of mild or greater at baseline
- Major vascular complications at 30 days
- Life-threatening or disabling bleeding at 30 days
- Alterra embolization at 30 days
- THV embolization at 30 days

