5 STUDY ENDPOINTS

5.1 Primary Endpoint

Main Cohort:

The primary endpoint is THV dysfunction at 6 months. THV dysfunction is defined as a non-hierarchical composite of:

- RVOT/PV reintervention
- Moderate or greater total PR via Transthoracic Echocardiography (TTE)
- Mean RVOT/PV gradient \geq 35 mmHg via TTE

PDS Registry:

The primary endpoint is Acute PDS Success, defined as a non-hierarchical composite of:

- Single THV implanted in the desired location
- RV-PA peak-to-peak gradient $<$ 35 mmHg post-THV implantation
- Less than moderate total PR by discharge TTE (or earliest evaluable TTE)
- Free of SAPIEN 3 / Alterra explant at 24 hours post-implantation

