7.4 Discharge

The following data will be collected for all subjects at discharge or within 48 hours prior to discharge, unless noted otherwise:

- Medications: Antithrombotics, antiarrhythmics, heart failure medications, antibiotics only
- 12-Lead ECG
- TTE
- Gated CTA: Must be performed after the valve implant procedure but prior to the end of the 30 days follow up period
- Chest X-Ray (CXR)
- Adverse events assessment

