7.5 Follow-up

The day of the valve implant procedure will be considered Day 0 and will be used to schedule all subsequent visits and calculate visit windows. Six months is defined as 180 days; one year is defined as 365 days.

7.5.1 30 days

The following assessments will be conducted at 30 days post-procedure (+ 14 days):

- Medications: Antithrombotics, antiarrhythmics, heart failure medications and antibiotics only

- NYHA Functional Class
- SF-36 health survey
- 12-lead ECG
- TTE
- Gated CTA: Must be performed after the valve implant procedure but prior to the end of the 30 days follow up period
- CXR
- Adverse events assessment

7.5.2 6 months

The following assessments will be conducted at 6 months post-procedure (+ 14 days):

- Medications: Antithrombotics, antiarrhythmics, heart failure medications and antibiotics only
- NYHA Functional Class
- 12-lead ECG
- TTE
- Fluoroscopy
- Adverse events assessment

7.5.3 12 months

The following assessments will be conducted at 12 months post-procedure (+ 30 days):

- Medications: Antithrombotics, antiarrhythmics, heart failure medications and antibiotics only
- NYHA Functional Class
- SF-36 health survey
- TTE
- cMRI
- Fluoroscopy
- Adverse events assessment

7.5.4 Years 2 through 5, 7 and 10

The following assessments will be conducted at years 2 through 5, 7 and 10 (+ 45 days):

- Medications: Antithrombotics, antiarrhythmics, heart failure medications and antibiotics only
- NYHA Functional Class
- TTE

- CXR or fluoroscopy. For subjects with a previously identified device fracture, fluoroscopy must be performed.
- Gated CTA – at years 5 and 10 only
- Adverse events assessment

7.5.5 Years 6, 8 and 9

The following assessments will be conducted by telephone or office visit at years 6, 8 and 9 (+ 45 days):

- Medications: Antithrombotics, antiarrhythmics, heart failure medications and antibiotics only
- Adverse events assessment

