| Type IIa | Wire fracture(s) resulting in loss of frame integrity ¹ without hemodynamic dysfunction ² or embolization | | | | | | | | | | | |
| Type IIb | Wire fracture(s) resulting in loss of frame integrity ¹ resulting in hemodynamic dysfunction ² without embolization | | | | | | | | | | | |
| Type IIIa | Wire fracture(s) with fragment separation resulting in embolization without hemodynamic dysfunction ² | | | | | | | | | | | |
| Type IIIb | Wire fracture(s) with fragment separation resulting in embolization and hemodynamic dysfunction ² | | | | | | | | | | | |
| Device Success | 
Device Success is defined as a composite of:
 
 • Single Alterra deployed into the desired location and • Single THV implanted in the desired location within the Alterra (staged procedures allowed) and • Right ventricle to pulmonary artery (RV-PA) peak-to-peak gradient < 35 mmHg post-THV implantation and • Less than moderate total PR by discharge TTE (or earliest evaluable TTE) and • Free of explant at 24 hours post-implantation | Sponsor | | | | | | | | | | |
| Device (Valve) thrombosis | Any thrombus attached to or near an implanted valve that occludes part of the blood flow path, interferes with valve function, or is sufficiently large to warrant treatment. Note that valve-associated thrombus identified at autopsy in a patient whose cause of death was not valve-related should not be reported as valve thrombosis | VARC-2 | | | | | | | | | | |
| Embolism | 
Embolism is defined as a free-flowing blood clot or lesion material that is located in the systemic or pulmonary circulation that occurs in the absence of infection after immediate perioperative period.
 
Pulmonary embolic event is an operative, autopsy or clinically documented embolus that produces symptoms from complete or partial obstruction of a pulmonary or bronchial artery
 | STS alignment | | | | | | | | | | |
| Explant | Removal of the Alterra for any reason | Sponsor | | | | | | | | | | |
| Index Procedure | Placement of Alterra Adaptive present study device and/or additional procedures (ex. placement of Sapien 3 valve) occurring in the catheter lab and/or operating room which are completed prior to subject transfer to a post-procedure recovery unit (e.g. Recovery Room, ICU/CCU, etc.) | Sponsor | | | | | | | | | | |

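### Acute PDS Success and Acute Device Success have no survival item, and the substitute TTE has no latest date, so an in-hospital death after one adequate TTE scores as a success

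*Combined protocol and SAP*

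**What the plan says.** Acute PDS Success is the registry's primary endpoint (synopsis, Sections 5.1 and 10.3). Its items are:

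- placement: "Single THV implanted in the desired location";
- an invasive RV-PA peak-to-peak gradient below 35 mmHg after the valve is implanted;
- PR: "Less than moderate total PR by discharge TTE (or earliest evaluable TTE";
- explant: "Free of SAPIEN 3 / Alterra explant at 24 hours post-implantation".

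Acute Device Success is an additional main-cohort outcome (synopsis, Section 5.3, and Appendix B under Device Success). It adds correct deployment of a single Alterra, keeps the same gradient and PR items, and ends with "Free of Alterra explant at 24 hours post-implantation".

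Appendix B defines explant as "Removal of the Alterra for any reason".

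The main cohort has a separate outcome, "All-cause mortality at 30 days and 6 months" (Section 5.3). The registry list in the same section has tricuspid regurgitation, vascular complications, bleeding and two embolization outcomes, but no mortality.

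The discharge TTE is taken "at discharge or within 48 hours prior to discharge, unless noted otherwise" (Section 7.4). The next scheduled TTE belongs to the 30-day visit: "The following assessments will be conducted at 30 days post-procedure (+ 14 days" (Section 7.5.1). The one after that is at 6 months, also with 14 days allowed.

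Section 10.3 assigns the Valve Implant population to the main cohort's primary endpoint. No population is named for either acute composite, and no rule covers a subject without an evaluable TTE.

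**The concern.** A reader takes an acute success rate to mean that the procedure worked and the patient came through it. As written, both composites are silent on survival. The only item with a time limit is explant at 24 hours, which concerns the device and not the patient. The worst procedural outcome can therefore be counted on the favourable side.

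The PR item raises a second problem. It accepts the first usable echo, however late. Balloon valvuloplasty and paravalvular leak closure are reinterventions under Appendix B, yet neither breaches an item of either composite. If the discharge TTE cannot be read, PR could be treated before the next TTE and the subject would still score as an acute success.

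At stake is the headline rate of the registry and one descriptive rate in the main cohort.

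**Working it through.** **The plan's own figures.** Neither composite has a stated target, expected rate or power. The figures in Section 10.1 belong to THV dysfunction at 6 months. With 38 subjects, the largest event count whose exact upper 95% limit lies below 25% is 4 (upper limit 24.8%). Then P(X ≤ 4 | n = 38, p = 0.25) = 0.0235 and P(X ≤ 4 | n = 38, p = 0.074) = 0.8531. Both match the plan. They do not involve either acute composite, so nothing below changes them.

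**Scoring a death under the written items.** Assume that the items not affected by the death are met.

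| Time of death | Single THV | Gradient | PR by TTE | No explant at 24 h | Result |
|---|---|---|---|---|---|
| Before THV implant | not met | none | none | not relevant | not a success |
| After implant, before any evaluable TTE | met | met | no value | met | not a success, but failure or dropped is not stated |
| After an evaluable TTE, before discharge | met | met | met | met | **success** |

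The first row assumes that the subject is in the denominator, which the plan does not settle.

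**Size in the registry (n = 25, Section 3).** Suppose one death and every other subject a success. Exact (Clopper-Pearson) limits are used to show scale; Section 10.3 plans descriptive tables only. When all n succeed, the lower limit is 0.025^(1/n).

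- Death scored as success: 25/25 = 100%; lower limit 0.025^(1/25) = 86.3%.
- Death scored as failure: 24/25 = 96.0%; limits 79.6 to 99.9%.
- Death dropped for want of a TTE: 24/24 = 100%; lower limit 0.025^(1/24) = 85.8%.

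The difference between success and failure is 1/25 = 4.0 points.

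**Size in the main cohort (n = 60 if all enrolled subjects are counted).** Scored as success: 60/60 = 100% (94.0 to 100%). Scored as failure: 59/60 = 98.3% (91.1 to 99.96%). The difference is 1/60 = 1.7 points.

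**Latest date of the PR result.** Section 7.5 sets Day 0 at the valve implant and 6 months at 180 days.

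- Discharge TTE not evaluable, 30-day TTE used: 30 + 14 = day 44.
- 30-day TTE also not evaluable, 6-month TTE used: 180 + 14 = day 194.

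**The case against.** The other side has a fair case. Both are success composites built on positive items, so many deaths already count against them or at least not for them. The case that remains is narrow: it needs a post-implant TTE before the death. Section 7.4 schedules that TTE for discharge or the 48 hours before it, and Section 7.3.3 relies on angiography and ICE during the procedure. A subject who dies early would usually need an unscheduled TTE to score as a success.

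Deaths are not lost either. An event leading to death is an SAE (Section 8.1), the CEC adjudicates device- and procedure-related events, the DSMB reviews study data, and main-cohort mortality is its own outcome. Survival could reasonably be kept out of a composite meant to describe device performance. Reaching day 194 needs two consecutive unusable TTEs despite standardized acquisition and training, and a later echo could show more PR as easily as less.

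Most of this stands as a limit on frequency and on harm in the main cohort. It does not remove the point for the registry. There the composite is the primary endpoint and no listed outcome counts deaths; safety reporting captures a death but does not put it beside the success rate. The scoring gaps are also not a matter of preference: two analysts could handle a death before any TTE differently, and both would be following the plan.

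**Conclusion.** The point holds as a definitional gap in both composites, chiefly for the registry. One in-hospital death after an adequate TTE moves the registry rate by 4.0 points and its lower exact limit from 86.3% to 79.6%, assuming that all other subjects succeed. In the main cohort the shift is about 1.7 points on a denominator of 60. The documents give no expected death rate, so these are sizes per event, not a forecast. The direction of any bias from a late TTE is not established.

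A reader might infer more than the documents support:

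- That death can never make either composite fail. A death before THV implant fails the single-valve item.
- That a death before any TTE counts as success. The PR item is then unmet; the plan leaves open only whether the subject fails or is dropped.
- That Acute Device Success is the main cohort's only procedural result. Section 5.3 also lists 30-day vascular complications, bleeding, embolization and mortality.
- That 38 is a possible denominator here. It is the observable sample for the 6-month endpoint.
- That the performance-goal test or type I error is at risk. Neither composite is formally tested.

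**What to change.** Make these changes in the synopsis, Sections 5.1, 5.3 and 10.3, and Appendix B, wherever each composite is stated:

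1. Add to both composites that the subject is alive at discharge from the valve implant hospitalization. Count a death before then as failure whether or not a TTE exists. Survival at 24 hours would not be enough, since a death on day 2 or later after an adequate TTE would still score as success.
2. Limit the substitute to the earliest evaluable TTE after THV implant, no later than the end of the 30-day window (day 44) and before any reintervention. This keeps one scheduled back-up echo. Stating that it follows THV implant also settles staged procedures.
3. In the main display, count a subject with no such TTE as not meeting the PR item. Show the evaluable-only rate as a sensitivity display. Making evaluable-only the main rule could be more lenient than the present text.
4. Report registry deaths at 30 days beside the success rate. This also covers deaths after discharge, which item 1 does not reach.
5. Name the denominator for each composite, so that a death before THV implant stays visible.

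The cost is wording and one extra line in the tables. No visit, test or subject is added. The reported success rate may be slightly lower.

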6 STUDY POPULATION

The study population will be comprised of subjects with a dysfunctional RVOT/PV, who are indicated for treatment of moderate to severe PR.

6.1 Inclusion Criteria

Candidates for this study must meet **all** of the following inclusion criteria to be eligible:

1. The candidate/candidate's legal guardian has been informed of the nature of the study, agrees to its provisions and has provided written informed consent
2. Weight is ≥ 20 kg (≥ 44 lbs)
3. RVOT/PV with moderate or greater PR by TTE
4. RVOT/PV proximal and distal landing zone diameter ≥ 27 mm and ≤ 38 mm, and minimum of 35 mm from contractile tissue to lowest pulmonary artery takeoff

6.2 Exclusion Criteria

Candidates will be excluded from the study if **any** of the following conditions are present:

1. Active infection requiring current antibiotic therapy (if temporary illness, patient may be a candidate 2 weeks after discontinuation of antibiotics)
2. History of or active endocarditis (active treatment with antibiotics) within the past 180 days
3. Leukopenia (White Blood Cell (WBC) < 2000 cells/ μ L), anemia (Hemoglobin (Hgb) < 7 g/dL), thrombocytopenia (platelets $< 50,000$ cells/ μ L) or any known blood clotting disorder
4. Inappropriate anatomy for introduction and delivery of Alterra or the SAPIEN 3 THV
5. Need for concomitant atrial septal defect or ventricular septal defect closure or other concomitant interventional procedures other than pulmonary artery or branch pulmonary artery stenting or angioplasty
6. Interventional/surgical procedures within 30 days prior to the Alterra or valve implant procedure
7. Any planned surgical, percutaneous coronary or peripheral procedure to be performed within the 30-day follow-up from the Alterra or valve implant procedure
8. History of or current intravenous drug use
9. Major or progressive non-cardiac disease resulting in a life expectancy of less than one year
10. Known hypersensitivity to aspirin or heparin and cannot be treated with other antiplatelet and/or antithrombotic medications
11. Known hypersensitivity to nitinol, cobalt-chromium, nickel or contrast media that cannot be adequately pre-medicated
12. Currently participating in an investigational drug or another device study [*Note: Trials requiring extended follow up for products that were investigational, but have since become commercially available, are not considered investigational devices.*]
13. Positive urine or serum pregnancy test in female patients of child-bearing potential
14. Renal insufficiency (creatinine > 3.0 mg/dL) and/or renal replacement therapy

7 STUDY PROCEDURES

7.1 Informed Consent

The study investigator(s) and support staff will approach patients with a dysfunctional RVOT/PV who are indicated for treatment of PR. They will assess their interest in participating in the study by providing them an overview of the study including the background, risks, benefits and study procedures. If patients are interested in participating in the study, they must sign the Institutional Review Board (IRB) / Ethics Committee (EC)-approved informed consent form (ICF) and screening will commence. Informed consent must be obtained prior to performing screening procedures or baseline tests that are not standard of care.

For those subjects whose initial consent was obtained from the legal guardian, a new consent must be obtained once the subject reaches adult age (if study participation is on-going), as determined by state and/or local laws. If the subject refuses to sign a new ICF, they will be withdrawn from the study.

All candidates being considered for study inclusion should be entered into the electronic database; the reasons for screen failure will be documented.

7.2 Screening/Baseline Assessments

The following data will be collected for all subjects \leq 30 days before the Alterra implant procedure, unless otherwise noted:

- Medical history
- Physical examination (blood pressure, heart rate, height, weight only)
- Medications – Antithrombotics (anticoagulants, antiplatelets, thrombolytics), antiarrhythmics, heart failure medications and antibiotics only
- New York Heart Association (NYHA) functional class
- Short form (SF)-36 health survey
- 12-lead electrocardiogram (ECG)
- TTE – Qualifying TTE must be performed within 90 days prior to the Alterra implant procedure.
- Gated computed tomography angiography (CTA) for general assessment of RVOT/PV, pulmonary artery and right heart anatomic parameters. CTA must be performed within 1 year prior to the Alterra implant procedure and meet the defined parameters within the applicable Core Lab Manual of Operations.
- Cardiac magnetic resonance imaging (cMRI) for general assessment of RVOT/PV and right heart function. cMRI must be performed within 1 year prior to the Alterra implant procedure and meet the defined parameters within the applicable Core Lab Manual of Operations.
- WBC, Hgb, hematocrit (Hct) and platelet count
- Serum creatinine

- Urine or serum pregnancy test for all females of childbearing potential
- International Normalized Ratio (INR), if subject is taking Warfarin (or other Coumadin derivative)

7.2.1 Case Review

All candidates being considered for participation must be approved by the Case Review Board. Before a case is submitted for review, the site will screen the candidate for initial enrollment criteria. Once fully screened and deemed an appropriate candidate, the site will submit the case for review and approval consideration by the Case Review Board.

Edwards will maintain a record of the case presentation and case review notes.

7.3 Procedure

7.3.1 Subject Enrollment

Subjects will be considered enrolled in the study after informed consent has been obtained and the Alterra procedure has begun (defined as the time of vascular access – incision or puncture). If these criteria are not met, the candidate will be considered a Screen Failure.

7.3.2 Recommended Concomitant Medical Therapy

Table 2 outlines the recommended concomitant medical therapy. It is expected that specific agents and dosing regimens may vary from site to site. It is strongly recommended that study subjects be treated prophylactically with antibiotics for endocarditis per the recommendation of the American Heart Association (9).

Table 2: Recommended Concomitant Medical Therapy

| | | |
|------------------------|--------------|--|
| Pre-procedure | Aspirin: | At least 81 mg within 24 hours prior to procedure |
| Intra-procedure | Antibiotics: | 1 st dose prior to or at time of procedure |
| | Heparin: | To achieve/maintain activated clotting time (ACT) \geq 250 sec |
| Post-procedure | Antibiotics: | 2 nd dose 8 hours after first dose 3 rd dose 8 hours following the 2 nd dose Prophylaxis for life |
| | Aspirin: | At least 81 mg once daily for life |

7.3.3 Implant Procedure

It is strongly encouraged that the Alterra procedure be performed within 14 days of case review approval.

Alterra may be implanted during the same procedure as the THV or in a separate, staged procedure. If staged, the valve implant procedure should take place no more than 3 months after the Alterra procedure.

The Instructions for Use (IFU) will be included with each shipment of the investigational devices. Study devices and accessories will be used per the most current labeling at all times. Only physicians appropriately trained to the use of the device and identified on the Delegation of Authority (DoA) log on file with Edwards may perform the implant procedures in study subjects.

Pre-implantation, the following assessments should be performed:

- Angiogram to evaluate coronary artery patency and aortic root configuration
- Intracardiac echocardiography (ICE) to assess native valve function, regurgitation, and native leaflet location and length (if present)

Post-implantation, the following assessments should be performed:

- Angiogram:
 - Evaluate deployment and positioning of the Alterra
 - Evaluate THV function and position within Alterra
- Invasively measure RV-PA peak-to-peak gradient, pulmonary artery pressure (PAP) and right atrium pressure (RAP)
- ICE to assess THV function, regurgitation, and native leaflet location and length (if present)

7.4 Discharge

The following data will be collected for all subjects at discharge or within 48 hours prior to discharge, unless noted otherwise:

- Medications: Antithrombotics, antiarrhythmics, heart failure medications, antibiotics only
- 12-Lead ECG
- TTE
- Gated CTA: Must be performed after the valve implant procedure but prior to the end of the 30 days follow up period
- Chest X-Ray (CXR)
- Adverse events assessment

